Annex 9- The Montreal Cognitive Assessment Scale

[figure not shown]
Annex 10: The Geriatric Depression Scale –version 15 items

Choose the best answer for how you have felt over the past week:

1	Are you basically satisfied with your life?	Yes	0
		No	1
2	Have you dropped many of your activities and interests?	Yes	1
_		No	0
3	Do you feel that your life is empty?	Yes	1
		No	0
4	Do you often get bored?	Yes	1
		No	0
5	Are you in good spirits most of the time?	Yes	0
		No	1
6	Are you afraid that something bad is going to happen to you?	Yes	1
		No	0
7	Do you feel happy most of the time?	Yes	0
		No	1
8	Do you often feel helpless?	Yes	1
		No	0
9	Do you prefer to stay at home rather than go out and do new things?	Yes	1
		No	0
10	Do you feel you have more problems with your memory than most?	Yes	1
		No	0
11	Do you think it is wonderful to be alive now?	Yes	0
		No	1
12	Do you feel pretty worthless the way you are now?	Yes	1
		No	0
13	Do you feel full of energy?	Yes	0
		No	1
14	Do you feel that your situation is hopeless?	Yes	1
		No	0
15	Do you think that most people are better than you are?	Yes	1
		No	0

Total score:

[figure not shown]
Annex 11- Quality of Life evaluation Visual Analogue Scale

Annex 12- Pain Evaluation Visual Analogue Scale

The worst pain imaginable	(
Т	\bigcirc
	(
No pain	\smile

Annex 13- Anxiety evaluation Visual Analogue Scale

4 / 8 4

Annex 14- The picture provided for written description

Annex 15- Data collection of written text (self-administration): Form given to the participant to fill in at home in case (s)he is capable of doing so

Dear Mr/Mrs

We are very interested in your writings and the way it can alter in time. In order to perform a text analysis we need you to provide us with some written texts, older and current.

[figure not shown]
- 1) Please prepare something **that you have written some time ago** to show to our colleague who will visit you at home
- 2) Please think, a major event of your life or anything else you like. For example you could **describe an enjoyable life** event like:

A wedding Your child's or grandchild's birth Some of your personal or your children's achievements An enjoyable travel experience Professional achievements Last time you felt excitement about a forthcoming event.

Or even an unpleasant even if you like.

Now please type in a text your thoughts. If it is not possible to type, then write it down by hand. If for any reason you are unable to write, then please, dictate it to our colleague who will visit you at home

3) Please, now type in **what you see in the picture**. If it is not possible to type, then write it down by hand. If for any reason you are unable to write, then please, dictate it to our colleague who will visit you at home

Annex 16- The Social Media Questionnaire

Given to the participant at the end to fill in at his/her home [Leave blank in database all unanswered questions]

Questionnaire for usage of the internet and social media

- This questionnaire is given and answered in a second time
- Administrated once during or after the first clinical assessment

Date administrated: ___/___ (dd/mm/yyyy)

1. Which means do you use to be kept updated and informed?

(more than one answer)

- 1. Television
- 2. Newspapers/magazines
- 3. Family/friends
- 4. Internet
- 5. Other.....

2. Do you use the internet?

[]No=1

[]Yes =2

If the answer is no, stop here

3. Do you consider yourself to be familiar internet user ?

- [] beginner =1
- [] less familiar =2
- [] very familiar=3

4. Which device do you usually use to connect to the internet?

(more than one answer)

- [] Computer/laptop 1=No, 2=Yes
- [] Tablet 1=No, 2=Yes
- [] Mobile Phone 1=No, 2=Yes

5. How often do you connect to the internet per week?

(the answer can be from 1 up to 7)

[] times per week

6. How many hours per day do you usually use the internet?

[] Hours per day

7. Which internet services do you usually use?

(more than one answer)

[] News/ Update/Information 1=No, 2=Yes

- [] Communication, Social media 1=No, 2=Yes
- [] Entertainment (games, music, TV, video) 1=No, 2=Yes
- [] Online Transactions 1=No, 2=Yes

```
[ ] Other: .....
```

8. Describe in a few words your 'internet' activity and the changes it has have brought upon your life

9. Do you use any social media (i.e. facebook etc)?

[]	No,	I have	never	used	them
---	---	-----	--------	-------	------	------

- [] No, i do not use them but i used to =1
- [] Yes I use the social media =2

Why did you stop;

If the answer is no, then stop here. Otherwise, continue further.

10. How long have you been using social media?

I have used social media for [] months

11. Which of the social media below do you use?

(more than one answer)

- [] Facebook 1=No, 2=Yes
- [] Twitter 1=No, 2=Yes
- [] YouTube 1=No, 2=Yes
- [] Instagram 1=No, 2=Yes
- [] Personal blog 1=No, 2=Yes
- [] Other:

12. How often do you use social media per week?

(the answer can be 1 up to 7)

[] times per week

13. When you use social media, how many hours per day do you usually use them for?

[] hours per day

14. What made you use social media for the first time?

15. Do you think that social media are easy to use?

- [] Very easy =1
- [] Easy =2
- [] Difficult =3
- [] very difficult =4

16. Do you consider yourself a familiar user of social media?

- [] Beginner =1
- [] Less familiar =2
- [] Very familiar =3

17. Which of the above information is included in your profile?

(more than one answer)

- [] Real name 1=No, 2=Yes
- [] e-mail 1=No, 2=Yes
- [] telephone 1=No, 2=Yes
- [] House Location 1=No, 2=Yes
- [] Photographs 1=No, 2=Yes
- [] Video 1=No, 2=Yes
- [] Religion 1=No, 2=Yes
- [] Interests 1=No, 2=Yes
- [] Other:.....

18. Does the information you provide on social medial represent reality and why?

- [] No =1
- [] Yes=2

Why:

.....

19. Fill in only if you use twitter, or otherwise go to question 22

How many followers you have on twitter?

[] (fill in a number)

20. How many people do you follow on twitter?

[] (fill in a number)

21. How often do you tweet per week?

[] (fill in a number)

22. How many friends/contacts do you have on facebook?

[](complete number) (Fill in only if you use facebook, otherwise go to question 24)

23. How many of your Facebook friends do you consider your true friends from all your friends/contacts?

[] Only a few =1
[] many of them =3
[] most of them =4
[] everyone=5

24. Do you accept friend requests from strangers at your social media accounts?

- [] never =1
- [] sometimes =2
- [] always = 3

25. What do you usually do during your social media visits?

(Fill in with numbers by beginning with 1 from the most frequent to the least frequent activity)

- [] post
- [] share
- [] like
- [] comment
- [] share a photo
- [] share a link
- [] share video/music
- [] other:.....

26. Do you follow politicians/organizations on social media?

- [] No =1
- [] Yes=2
 - 27. Do you believe that communication between politicians and voters through social media is important?
- [] Strongly agree=1
- [] Agree=2
- [] Disagree=3
- [] Strongly disagree=4

28. What type of pages you follow at social media?

.....

29. Do you believe that social media affect your social life

- [] very positively =1
- [] positively =2
- [] Do not affect at all =3
- [] Negatively =4
- [] Very negatively =5
 - 30. Besides the activity of yourself and of your contacts, is there anything else that draws your attention in social media? (i.e. Advertisements, offers etc)? How do you respond to this? Does it affect your judgment in some degree?

.....

31. Do you think that there is a danger for the safety of your personal data in social media?

```
[] Strongly agree =1
```

[] agree=2

[] disagree=3

[] strongly disagree =4

[] I don't know/doesn't concern me=5

32. Do you believe that the privacy policies of the social media that you are using are effective?

[] Strongly agree=1

[] I agree=2

[] I don't know/it doesn't concern me=3

33. Are you aware of who can check your profile and the information it contains in the social media you are using?

[] No=1

[] yes=2

[] I don't know / it doesn't concern me=3

34. Have you changed your security settings in social media in order to protect your personal data?

[] No=1

[] Yes=2

Annex 17- The Big five questionnaire

In order to be recognized the traits Big Five model each person should answer in the following Likert scale a questionnaire which includes 44 questions.

Strongly Disagree $\rightarrow 1$ Disagree a little $\rightarrow 2$ Neither agree nor disagree $\rightarrow 3$ Agree a little $\rightarrow 4$ Strongly Agree $\rightarrow 5$

The questions are the following:

I see myself as someone who ...

- ____1. Is talkative
- ____2. Tends to find fault with others
- ____3. Does a thorough job
- ____4. Is depressed, blue
- ____5. Is original, comes up with new ideas
- ____6. Is reserved
- ____7. Is helpful and unselfish with others
- ____8. Can be somewhat careless
- ____9. Is relaxed, handles stress well
- ____10. Is curious about many different things
- ____11. Is full of energy
- ____12. Starts quarrels with others
- ____13. Is a reliable worker
- ____14. Can be tense
- ____15. Is ingenious, a deep thinker
- ____16. Generates a lot of enthusiasm
- ____17. Has a forgiving nature
- ____18. Tends to be disorganized
- ____19. Worries a lot

- ____20. Has an active imagination
- ____21. Tends to be quiet
- ____22. Is generally trusting
- ____23. Tends to be lazy
- ____24. Is emotionally stable, not easily upset
- ____25. Is inventive
- ____26. Has an assertive personality
- ____27. Can be cold and aloof
- _____28. Perseveres until the task is finished
- ____29. Can be moody
- ____30. Values artistic, aesthetic experiences
- ____31. Is sometimes shy, inhibited
- ____32. Is considerate and kind to almost everyone
- ____33. Does things efficiently
- ____34. Remains calm in tense situations
- ____35. Prefers work that is routine
- ____36. Is outgoing, sociable
- ____37. Is sometimes rude to others
- ____38. Makes plans and follows through with them
- ____39. Gets nervous easily
- ____40. Likes to reflect, play with ideas
- ____41. Has few artistic interests
- ____42. Likes to cooperate with others
- ____43. Is easily distracted
- _____44. Is sophisticated in art, music, or literature

Annex 18- Form of traceability of blood sampling destined to telomeres analysis

Sensing and predictive treatment of frailty and associated co-morbidities using advanced personalized models and advanced interventions

Principal Investigator:

ID : Laboratory examination: Measurement of telomeres' length Date of blood sampling: Prescriber physician:	Comments :
Drawn on at	
 Patient's consent given EDTA tube Conservation at 4°C during the transport Time limit until freezer respected (3 hours max) 	

Copy for the laboratory

Sensing and predictive treatment of frailty and associated co-morbidities using advanced personalized models and advanced interventions

Principal Investigator :.....

ID : Laboratory examination: Measurement of telomeres' length Date of blood sampling: Prescriber physician:	Comments :
Drawn on	
 Patient's consent given EDTA tube Conservation at 4°C during the transport Time limit until freezer respected (3 hours max) 	

Copy to be stored in the patient's folder

Annex 19- Operational procedures' check lists

A. Clinical Evaluation Visit

The participant should be asked to bring:

- \checkmark A medication prescription or the boxes of the medication they take
- ✓ Samples of older written texts they produced
- ✓ Their glasses and/or their hearing aid
- ✓ Comfortable shoes
- ✓ Their walking aid if there is one

The investigator should make sure that the "clinical evaluation visit kit" contains:

- ✓ Papers/ questionnaires/ consent forms
- ✓ Pens
- ✓ Pencil (for the MMSE)
- ✓ Watch (for the MMSE)
- Measure tape (for body circumferences measurements and the definition of the 3 meter distances for the gait tests)
- ✓ Electronic scale
- ✓ Stopwatch (for gait tests)
- ✓ Electronic tensionmeter
- ✓ Mobilograph
- ✓ Tablet(with internet connection)+ charger
- ✓ Dynamometer + batteries
- ✓ Ruler (to quantify the VAS)
- ✓ IMUs

B. The FrailSafe session home visit

The nurse should make sure that for each visit the "FS home suitcase" contains:

- ✓ Her own smartphone
- ✓ The smartphone for the participant +charger
- ✓ Some phone cases in order the participant to choose which one suits him/her best
- ✓ The WWS device (straps): if should be cleaned +charger
- ✓ The tablet +charger
- ✓ The dynamometer
- ✓ The tensionmeter
- ✓ The beacons
- ✓ The AR glasses
- ✓ The plug adaptors needed for some devices (WWS electronic box, smartphones etc)
- ✓ The power strip for multiple plug charging

- ✓ Batteries
- ✓ Measure tape (in case some gait tests are required)
- ✓ Stopwatch (in case some gait tests are required)
- ✓ Paper/pen material in case of written text dictation
- ✓ Blood sampling material (only for the first visit)
- ✓ Any educational and informative material each center prepares to facilitate the education of the participants in the use of the FS system material
- The housing evaluation questionnaire and phone follow up questionnaires in paper form
- ✓ Disinfecting product to clean up the devices if needed

Note: in case of more than one FS home visits per day, this material should be multiplied accordingly

Tasks and actions in practice:

Before the visit

- ✓ Contact the participant and fix the appointment for the FS visit
- ✓ Verify that all required material are available and ready for use

During the installation visit

- ✓ Blood sample (only first visit)
- Explication of the use, the purposes and the technical issues of the FrailSafe material: educate the participants and check their comprehension
 - WWS:
 - i. Put on-put off demonstration
 - ii. Instructions for the recommended use and duration
 - BP device
 - i. Explication of the conditions of BP measurements
 - Tablet
 - i. Demonstration of the virtual games
 - Dynamometer
 - i. Demonstration of the game
 - Smartphone + phone case
 - i. Explication of the importance of carrying around the smartphone as continuously as possible
 - AR glasses
 - i. tests performed during the nurse's presence
 - ii. demonstration of games to play on their own
 - Beacons
 - i. Installation in rooms
 - ii. Verification of their connectivity to the smart phone

- iii. Write down the coordinates of the placement
- ✓ Education on the charging of the various material + provide with some extra batteries
- Provide the participant with written instructions about the use the material and with contact details in case its needed
- ✓ Collect any questionnaires filled in by the participant since the last visit, ex written texts, social media questionnaires or help him/her write the text
- ✓ Fill in the "phone" follow up questionnaire
- ✓ Fill in the questionnaire regarding the participant's housing
- ✓ Complete any missing information of the clinical evaluation ex prescription photo, older written text photo
- ✓ Before leaving verify the connectivity and the well-functioning of all material
- \checkmark Set the next appointment to retrieve the FS material (5th day)

During the session period

- ✓ Telephone Follow-up **during** the instauration of the FS system in an everyday basis to catch up with the experience of the use of the material
- ✓ On call availability to resolve any issues
- ✓ Possibility for additional visits between the installation and the retrieval if needed

During the material retrieval visit

- ✓ Retrieval of all material left at the participant's house
- ✓ Satisfaction questionnaire

After the session

- ✓ Upload total trial data from all measurements (internet needed).
- ✓ Restore and clean all material used

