3.5 Blood tests

In the beginning of the study, along with the first clinical assessment appointment and the first FrailSafe system home visit, a blood sampling will take place for telomeres measurement. After following a standard sampling procedure, all samples will be sent and processed in INSERM's laboratory in Nancy, France, along with their traceability accompanying form (Annex 18). Telomere length will be measured in DNA extracted from white blood cells, with the southern blot method (46) which is the most reproducible method for measuring telomeres length (47).

Presence of short telomeres is associated with various age-related degenerative diseases (48, 49). Recent studies indicate that short telomere length is not only a biomarker but a significant bio-determinant of such diseases (46, 49). The present study will assess the hypothesis that measurements of telomere length may provide further information in the characterization of frailty in older subjects.

A second blood taking will be realized only in the center of the University of Patras in M27 for group A, in M25 for group B and in M35 for group C. The immune system alterations observed in frailty are multifaceted and associated with increased morbidity and mortality in older adults (50, 51). The identified alterations include heightened inflammation and alterations in the innate and adaptive immune systems. The heightened inflammatory state includes increased levels of inflammatory molecules (IL-6 and CRP) and increased counts of

white blood cells and their subpopulations. These changes may play an important role in the pathogenesis of frailty, directly or through its influence to other physiologic systems (52-54). A subgroup of participants, men and women in UoP, will be tested for their immune system and inflammatory profile, vitamin D levels, and endocrine system function (54)(IGF-1, sex hormones). Complementary biological tests can be proposed according to newest data of the international literature in the field of frailty and the availability of biological material. The aim of the study is the analysis of immunological changes during senility and age-related markers of inflammation which may provide useful prognostic markers of morbidity and mortality. The characterization of elderly people with higher risk factors might allow for preventive and/or therapeutic measures to assure successful ageing and survival and to stem the rapid progression of the ageing process.

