3.7.8 FrailSafe system's application standardization

As predicted by the initial proposal and its amendments, not the totality of the FrailSafe system devices was available since the beginning of the clinical study.

Therefore, we noted a quite important heterogeneity among the first FrailSafe sessions conducted in the centres of Patras and Cyprus. In order to address this source of bias, the

very first participants for whom the FrailSafe session was incomplete according to some minimum requirements (enlisted bellow), will be called back in order to repeat the session.

The FraiSafe system devices which are currently available and are going to be used in all FraiISafe sessions (=home visits), from now until new versions of devices arrive, are:

- The tablets with virtual reality games (for all participants)
- The smartphones with the GPS application (for all participants)
- The blood pressure monitoring devices (for all participants)
- The WWS devices (strap version) (for 1 participant at a time)
- The dynamometers for grip strength games' playing (for all participants)
- The beacons (for all participants).

Towards the direction of standardizing the procedures and adapting the material to the actual needs of the participants, working documents treating practical issues such as study's material, anticipated and actually occurring problems and procedures have been generated and are being constantly updated. Similarly, detailed check lists about the material, requirements and conditions to be verified before, during and after the clinical evaluation and the FrailSafe home visits have been distributed in the 3 clinical centres (Annex 19).

4. Operational procedures per group

In a more concentrated and systematic way the operational procedures per group are as following:

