- 10. Daily phone calls during the instauration of the FrailSafe system to catch up with the experience of the use of the material and any problems that may have arisen
- 11. Short satisfaction interview in the day of FrailSafe system retrieval
- 12. Telephone Follow-up after the retrieval of the FrailSafe in a 3 months' basis (table 17). (M9-M24)
- 13. Second clinical evaluation (M27) (tables 5-14)
- 14. Data collection of written text after the first time (table 16) (M27). The participant will either be helped to provide text by dictation or be asked to prepare it him/herself in his/her home and deliver it to us in the next appointment
- 15. Second FrailSafe system instauration (M27)
 - [Only for Patras]: blood sampling
 - Fill in the evaluation form regarding the participant's housing (table 18)
 - Collect any questionnaires filled in by the participant since the last visit (written texts)

- Complete any missing information of the clinical evaluation (i.e. scanning of a forgotten prescription, scanning of an older written text provided by the participant, write down dictated text)
- Administration of follow up questionnaire (table 17)
- Installation of the currently available FrailSafe system and reminding of the use, the purposes and the technical issues of the FrailSafe material (Session 3.8). Verification of its correct function
- Provide contact details and instructions in case of any help needed
- Set the next appointment to retrieve the FrailSafe material (5th day)
- 16. Maintenance of the FrailSafe system at home during 3-5 days
- 17. Daily phone calls during the instauration of the FrailSafe system to catch up with the experience of the use of the material
- 18. Telephone Follow-up after the second retrieval of the FrailSafe (M30) (table 17)
- 19. Last clinical evaluation (M33) (tables 5-14)
- 20. Data collection of written text after the first time (table 16) (M33). The participant will either be helped to provide text by dictation or (s)he will write it down during the clinical assessment appointment
- 21. Last telephone follow up M36
- 22. Study's completion verification (table 20). Normally at the end (M36), but could be in anytime in case of premature withdrawal.

Did the patient complete the study as predicted?	1. Yes 2. No

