4.5 Group D- Control

- 1-5. As described above for all groups
- 6. Complete clinical evaluation session (tables 5, 7, 8, 10, 11, 12, 14) (M31)
- 7. Blood sampling for telomeres (M31)
- 8. One follow-up telephone call (M33)(table 17)
- 9. Last clinical evaluation (M36) (tables 5-14)
- 10. Data collection of written text after the first time (table 16) (M36). The participant will either be helped to provide text by dictation or (s)he will write it down during the clinical assessment appointment.
- 11. Study's completion verification (table 20). Normally at the end (M36), but could be in anytime in case of premature withdrawal.

5. Architecture of data analysis

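### Annex 19 limits home-visit blood sampling to the first visit, but section 4.2 schedules a Patras draw at group A's second home installation

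*Protocol*

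**What the plan says.** Annex 19 B of the protocol is the checklist for the FrailSafe home visit. Its suitcase list, which the nurse is to check for every visit, includes "Blood sampling material (only for the first visit". Its list of tasks at the installation visit includes "Blood sample (only first visit". Neither line mentions Patras. Section 3.7.8 says that the checklists "have been distributed in the 3 clinical centres (Annex 19", so Patras staff hold the same list as everyone else.

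Section 3.5 describes two draws. At the first, "a blood sampling will take place for telomeres measurement". The next paragraph opens with the second: "A second blood taking will be realized only in the center of the University of Patras", at M27 for group A, M25 for group B and M35 for group C. Later in that paragraph comes "A subgroup of participants, men and women in UoP, will be tested for their immune system and inflammatory profile", followed by vitamin D and endocrine measurements. Section 2.5 confirms that the second draw is for a subgroup of Patras participants and does not give its size.

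Section 4.2, step 15, is group A's second FrailSafe installation at home. Its first item is "Only for Patras]: blood sampling".

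**The concern.** A packing list that rules out sampling material after the first visit decides whether a sample can physically be taken. If the nurse arrives at the second installation without tubes, remembering section 4.2 on the spot does not help. By the schedule in section 4.2 this is group A's last home installation, so no later installation visit would catch the omission.

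At stake is a single-centre laboratory sub-study. Each selected group A participant whose second draw is missed would have no second sample. The second draw is the only one that section 3.5 places alongside the immune and endocrine tests; the traceability form in Annex 18, used for the first draw, names telomere length alone.

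**Working it through.** No design figure is involved, so the check sets the instructions side by side.

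**1. Group A, Patras.**
- Annex 19 B: sampling material and blood draw at the first home visit only.
- Section 4.2, step 8: first home visit, telomere draw. This agrees with the checklist.
- Section 4.2, step 15: second home installation, Patras blood sampling. This conflicts with both checklist lines.

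**2. How many participants the conflict can reach.** Section 2.3 gives group A the serial numbers 001 to 080 at each centre, so Patras group A has 80 planned participants. The second draw covers an unstated part of them, so the number exposed is at most 80 and may be much smaller.

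**3. Groups B and C, Patras.**

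| Group | Second draw | Where section 4 puts it | Nearby visits |
|---|---|---|---|
| B | M25 | Section 4.3, step 21, a step of its own | Home cycle B6 at M24-25 (section 2.6); clinical evaluations at M10, M16, M22, M35 |
| Ci | M35 | Section 4.4.1, step 14, a step of its own | Home visit at M35 (step 13); clinical evaluation at M36 |
| Cii | M35 | Section 4.4.2, step 11, a step of its own | One installation, at M31, for 60 days; clinical evaluation at M36 |

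None of these draws is an item of a home visit, so Annex 19 B does not contradict them. Their setting is simply not stated. The clinical-evaluation kit in Annex 19 A lists no blood material. If the group B or Ci draw is meant to happen at the home visit in the same month, the checklist would need the same correction there.

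**4. When group A's second session takes place.** Section 2.5 gives M26 for the session and M27 for the blood. Section 4.2 gives M27 for both. The modified timetable in section 2.6 gives M28-30 for the second cycle. The one-month tolerance in section 2.5 does not bring these together: M26 plus one month is M27, short of M28, and M27 plus one month is M28, short of M29-30. A corrected checklist that referred staff to a month would still not identify the visit.

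**5. Time left.** Section 2.6 says the revision was written at the beginning of M23. The earliest second draw is group B's at M25, so the correction can precede all of them.

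**The case against.** The strongest reply is that Annex 19 is a generic list for three centres and that Patras-only work is specified elsewhere. The autonomic tests and the MRI or DEXA scans are also Patras-only, appear in no Annex 19 list, and nobody would conclude that they are cancelled. Section 4.2 tells Patras staff explicitly to draw blood, and section 3.7.8 describes working documents that are kept updated. A nurse who noticed the omission could also draw the sample at the retrieval visit or at an extra visit, which Annex 19 allows during the session.

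Much of this stands, and it keeps the point small. It does not remove the conflict. The scans and autonomic tests are unlisted, whereas a second-visit blood draw is expressly excluded by the word *only*, in two places, in the list used to pack for the visit.

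Three stronger readings are tempting, and the protocol does not support them:
- A reader might infer that the sub-study would collect no samples at all. The group B and C draws are separate steps that the home-visit checklist does not cancel.
- A reader might add the Patras groups, 80 + 40 + 25 = 145, and call all of them affected. The direct conflict concerns group A only, and within it only a subgroup of unstated size.
- A reader might think group D's telomere sample is at risk, because group D has no home visit and Annex 19 A lists no blood material. Section 2.5 schedules that draw together with the M31 clinical evaluation, and section 4.5 lists it as "Blood sampling for telomeres (M31". Its absence from a packing list is missing detail, not a contradiction.

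**Conclusion.** The contradiction is real and narrow. Annex 19 B and section 4.2, step 15, give opposite instructions for blood sampling at group A's second home installation in Patras. Staff following the checklist alone would miss that draw for the selected subgroup, at most 80 participants.

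The conclusion rests on two assumptions. First, the nurse packs from Annex 19 without a separate Patras instruction; the protocol mentions other working documents but does not show them. Second, the immune, inflammatory, vitamin D and endocrine tests use the second draw. Section 3.5 implies this by placing both in one paragraph and does not say it outright.

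The blood tests do not enter the hard or proxy outcomes, the components of the clinical and technical frailty indices, or the hypotheses in Table 24, so the main analyses are unaffected. This is an operational inconsistency in a single-centre sub-study, worth correcting because the correction is nearly free and still in time.

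**What to change.** 1. In Annex 19 B, change both lines to read: first visit (all centres) and, in Patras, group A's second FrailSafe installation visit for participants selected for the second sampling. Tie the wording to the visit, not to a month.
2. State in sections 4.3, 4.4.1 and 4.4.2 at which visit the Patras group B, Ci and Cii second draws take place, and list the sampling material in the checklist for that visit.
3. Reconcile the month of group A's second session across sections 2.5, 2.6 and 4.2.
4. Reissue the checklist to the centres before M25.

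The cost is two edited checklist lines, a stated setting and material entry for the group B and C draws, and one reconciled date. No procedure is added, because every draw concerned is already planned.
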